6.7 Risk-to-benefit rationale

This is a low risk device and potential benefits outweigh risks by reducing pain and improving quality of life.

7 Objectives and hypotheses of the clinical investigation

7.1 The purpose of the clinical investigation, claims for clinical performance, effectiveness or safety of the investigational device that are to be verified.

Pain relief, reduction in stiffness, further highlight efficacy of the device for pain relief. No safety aspects will be verified.

7.2 Objectives, primary and secondary – superiority.

a) Primary objective

The main objective of the study is to assess the efficacy of the new wearable TENS device to reduce OA knee pain and further confirm the usability of the device at home over a longer period.

b) Secondary objectives

As secondary objectives the trial will evaluate:

- Changes in functional outcomes observed in the intervention group (TENS arm) and control group (Sham arm),
- Effect of using the knee wearable sleeve on health care utilization, and
- Usability of the prototype over a longer (12 week) period.
- 7.3 Scientific justification and clinical relevance for effect sizes, non-inferiority margins or equivalence limits, where applicable.

Not applicable.

7.4 Primary and secondary hypotheses, if applicable.

- The e-textile wearable TENS is able to reduce pain for people with knee OA.
- The device is suitable for home use in terms of user comfort, ease of use, and safety (e.g. no adverse events).
- The device may improve the functions measured via the Oxford Knee Score, Western Ontario and McMaster Universities Arthritis Index (WOMAC), EuroQol-5 Dimensions-5 Levels (ED-5Q – 5L), and Modular Resource Use Measure (ModRUM).

7.5 Risks and anticipated adverse device effects that are to be assessed.

Risk: Minor skin irritation. No adverse device effects anticipated.

8 Design of the trial investigation

8.1 Description of the design type of clinical investigation to be performed (e.g. randomised, blinded or open-label, parallel groups or crossover, multicentre, international) the control group, (e.g. comparative claim and reversible treatment of a chronic state) and the comparator with rationale and justification for the choice. Absence of control(s) shall be justified.

This is a double-blind 2-arm parallel group randomised controlled trial of 80 people comparing the efficacy on knee pain relief in patients with medically-diagnosed knee osteoarthritis. 80 people will be randomly allocated in a 1:1 ratio to the intervention arm (an active TENS group) or to the sham (control) group who will have TENS programmed to switch off automatically after an initial 4 minutes of stimulation.

8.2 Description of the measures to be taken to minimize or avoid bias, such as randomisation, concealment of allocation, blinding/masking, and management of potential confounding factors.

Participants will be randomly allocated to treatment or control (sham treatment) in a 1:1 ratio according to a randomisation schedule held by the statistician. The schedule will be based on a block randomisation with varying block sizes to avoid imbalance in treatment allocation with respect to known and unknown confounders, and to avoid any potential for anticipation of future participants' treatment allocation.

8.3 Primary and secondary endpoints, with rationale for their selection and measurement. If applicable, composite endpoints, with rationale for their selection and measurement.

To evaluate efficacy of TENs on knee pain relief we will collect data on: knee pain recorded on a Visual Analog Scale, and WOMAC-pain sub-scale.

Secondary outcomes of the study include the Oxford Knee Score, Western Ontario and McMaster Universities Arthritis Index, EuroQol-5 Dimensions-5 Levels, Modular Resource Use Measure and a list of adverse reactions.

A detailed list of the outcome measures is included in the Investigator Brochure - document 3.

8.4 Methods and timing for assessing, recording, and analysing variables.

Clinical outcomes will be reported on paper questionnaires. We will collect baseline information prior to supply for the intervention/sham device. Follow up data will be collected at 1, 4, 8 and 12-weeks after supply of the wearable device. Phone calls to supplement data collection at weeks 1, 4 and 8 will be employed as appropriate.

Data from paper questionnaires will be doubled entered onto a database at the MRC LEC and then transferred to the statistician for analysis.

8.5 Equipment to be used for assessing the clinical investigation variables and arrangements for monitoring maintenance and calibration.

Not applicable.

8.6 Any procedures for the replacement of subjects.

Not applicable

8.7 Investigation sites: number, location, and, if appropriate, differences in investigation site environment.

The study will be conducted at Southampton General Hospital, a large tertiary referral hospital in the United Kingdom, the E-Textile Innovation Laboratory at University of Southampton, Winchester School of Art and within the participants home setting.

8.8 Definition of completion of the clinical investigation (see 8.1).

The completion of the clinical investigation is defined by the conclusion of home use for 12 weeks and the return of the garment/device to the investigation site at the end of that period.

9 Trial Participants

9.1 Inclusion criteria for subject selection.

People will be able to take part in the study if they comply with the following:

- Adults between 45 and 75 years of age,
- Diagnosed with knee OA according to American College of Rheumatology criteria,
- Pain score ranging from 3 to 7 on the Visual Analog Scale (VAS)
- Participants will not have prior experience of TENS or other electrotherapy (e.g. interferential therapy)
- Able to stand up unaided, and
- Willing and able to give informed consent.

9.2 Exclusion criteria for subject selection.

- Prior major knee surgery (i.e., partial or total knee arthroplasty),
- Anticipated surgery during the study (no anticipated surgery during the 12 weeks of the study),
- Skin sensitivities and sensation problems,
- Uncontrolled epilepsy,
- Those who are pregnant; planning to become pregnant or are breastfeeding,
- An active device implant (e.g. pacemaker user),
- A stent in the lower limb.
- Inability to understand English
- Intra-articular injection to the knee

Oral medication for knee pain (paracetamol, NSAIDS, opiate based medication) will be allowed but it will be recorded.

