Primary Objective	To assess the efficacy of the new wearable TENS device to reduce OA knee pain and further confirm the usability of the device at home.			
Secondary Objectives	Changes in functional outcomes observed in the intervention group (TENS arm) and control group (Sham arm), Effect of using the knee wearable sleeve on knee function, health care utilisation, usability of the prototype at home over a 12 week period			
Rationale	Osteoarthritis (OA) is the most common musculoskeletal condition, with painful knee OA being highly prevalent. While people with knee OA who exercise regularly experience less pain and improved physical function, pain typically reduces physical activity, which is linked to a range of adverse health events. Knee pain is traditionally managed using medication (NSAIDs/opioids), which costs the UK £195.3 million p.a.; however these medications can cause side effects.			
	TENS is a non-pharmacological treatment that may be beneficial for pain relief, reduction of stiffness, and improvement of knee joint function. Previous research studies have highlighted a possible role for TENS in the management of painful knee OA. However, methodological concerns remain about how to use this technology optimally.			
	Our research team has developed a wearable garment with two pairs of integrated TENS electrodes around the knee together with a TENS electronic control unit. Following laboratory and home usability studies we now wish to perform a pilot RCT to inform the design of a future trial by estimating the variability of pain reduction and functional outcomes of TENS use.			
Project Observational study / Superiority Trial Design/ Classification				
Study Population	Patients with diagnosed Knee Osteoarthritis			
Total No. of Sites	1 (UHSFT)			
Study Duration	9 months			

Data collection	Data on socio-demographic and clinical characteristics, pain, function, skin reaction, medication taken, use of assistive devices, and any adverse reaction will be collected as shown in Table 1. Medication use will be recorded at each time point, with indication. Adverse events will be recorded at each time point. Safety reporting will follow GCP guidance with suspected unexpected serious adverse reactions reported to the MHRA.
Number of Participants	80 = 2 cohorts of 40 (intervention and sham)
Primary endpoint To evaluate efficacy of TENs on knee pain relief we will collect data on: the V Scale, and WOMAC-pain sub-scale.	

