The primary analysis will compare the primary outcome measures (knee pain) in mixed-effects linear regression models to account for repeated measures from baseline to 12-weeks follow-up, with treatment arm as a fixed effect along with other potential important baseline factors such as socio-demographic and clinical characteristics. Recruitment and retention rates will be summarized overall and presented with 95% confidence intervals.

12.4 The significance level and the power of primary endpoint(s) and the overall statistical testing strategy, if applicable.

A significance level of 5% and power of 80% will be used.

- 12.5 Sample size calculation and justification taking into account:
- 12.5.1 All relevant clinical data on outcome variable and effect size, if applicable

These will be explored in this study.

12.5.2 Assumptions of expected outcomes across treatment groups, if applicable.

Not applicable.

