12.5.3 Adjustments due to any pre-planned interim analyses, if applicable

Not applicable. There will be no interim analyses.

12.5.4 Detectable effect size and non-inferiority margin, which shall be smaller than the detectable effect size and justified with reference to the effect of the comparator, if applicable;

Non-inferiority margin is not applicable. Detectable effect size is a standardized effect size of 0.69.

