12.5.5 Randomisation allocation ratio

Ratio = 1:1

12.5.6 Expected drop-out rate, such as withdrawal, lost to follow-up, death (unless death is an endpoint).

80 participants will be recruited into the study, 40 to each treatment arm. We will recruit 80 participants (40 per trial arm) to achieve a sample size of N=70, 35 in each treatment arm, allowing a 12.5% drop-out rate. We anticipate that our drop -out rate will be lower than our original, conservative, estimate of 25%. However,

if we do not achieve a sample of N=70 (35 in each treatment arm) complete data by recruiting 80 participants, we will continue to recruit until we have achieved our planned N=70 participants with complete data.

12.5.7 All the statistical parameters and methods used to calculate sample size or the non-inferiority margin shall be clearly provided.

We will assess the efficacy of the new TENS wearable device to reduce OA knee pain. A sample size of complete data of N=70 (35 in each treatment arm) will allow us to detect a standardized effect size of 0.69, with 5% significance level and 80% power.

Additionally, our sample size calculation has been calculated assuming this is a pilot randomised controlled trial that will gather data to inform a future definitive trial. Teare et al [15] conducted an extensive simulation study considering the precision gained per additional 5 patients in the estimation of the variability of a continuous normally distributed outcome. Their work demonstrated that a total sample size of 70 is required to estimate the variability of a continuous outcome to have adequate data to inform the sample size for a fully powered definitive RCT, with a sample size above 70 yielding little additional precision. Thus, this sample size will allow us to estimate the variability of the primary outcome to inform a future definitive RCT.

12.6 Rationale for the number of procedures to be performed by a single user as part of the learning curve and how these data are to be analysed, if applicable.

Not applicable.

12.7 Pass/fail criteria to be applied to the results of the clinical investigation.

Not applicable

12.8 The provision for an interim analysis, criteria for the termination of the clinical investigation on statistical grounds, where applicable.

Not applicable

12.9 Management of bias and, when randomisation, matching, or blinding are applied, plan for assessment of success thereof.

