We will compare baseline characteristics as an assessment of the success of the randomisation. No formal statistical tests will be used to compare baseline characteristics between the randomised treatment groups.

12.10 Management of potential confounding factors (e.g. adjustment, stratification, or stratified randomisation).

Potential confounding factors such as baseline clinical characteristics will be adjusted for as fixed effects in mixed-effects linear regression models.

12.11 Description of procedures for multiplicity control and adjustment of error probabilities, if applicable.

Not applicable.

12.12 Specification of subgroups for analysis, if applicable, or if response to treatment is expected to be different in these groups.

Not applicable.

12.13 Management, justification, and documentation of missing, unused or spurious data, including drop-outs.

All efforts will be made to collect complete data. An assessment on the amount of missing data, especially in the primary outcome, will be made. We will consider whether data are missing not at random. Multiple imputation methods will be considered if <10% of the primary outcome data are missing (at random).

12.14 Exploratory analysis and sensitivity analysis (e.g. to explore robustness of results of primary and secondary analysis with respect to different methods used for handling missing data), if applicable.

Not applicable

12.15 Procedures for reporting any deviation(s) from the original statistical analysis plan.

These will be reported according to CONSORT guidelines.

12.16 For multicentre clinical investigations, a strategy for handling the potential imbalance of the numbers of subjects across investigation sites.

Not applicable

12.17 A strategy for pooling data, if applicable.

Not applicable.

13 Data Management

13.1 Methods (e.g. CRF) for data entry and collection.

The questionnaires will be completed in paper format. They will then be double data entered by Data Processing Assistants at the MRC LEC. Monitoring by PHARMExcel will occur throughout the study to ensure that issues and data queries are dealt with promptly, details will be contained in a study specific monitoring plan.

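### Two unranked primary pain measures share one 5% level and one 80% power figure, with multiplicity entered as not applicable, so the two figures cannot both be assured for an overall efficacy claim

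*Protocol*

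**What the plan says.** The synopsis row for the primary endpoint names a pain scale (its label is damaged in the text at hand, but it is evidently the VAS) together with the WOMAC pain sub-scale. Section 8.3 repeats the pair: "we will collect data on: knee pain recorded on a Visual Analog Scale, and WOMAC-pain sub-scale". Neither place ranks them.

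Section 12.3 uses the plural: "The primary analysis will compare the primary outcome measures (knee pain) in mixed-effects linear regression models". Sections 12.1, 12.5.7 and 12.13 speak of the primary outcome in the singular, so the protocol is not consistent about how many primaries there are.

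Section 12.4 reads "A significance level of 5% and power of 80% will be used". Section 12.5.4 adds "Detectable effect size is a standardized effect size of 0.69", and section 12.5.7 says that 35 complete participants per arm "will allow us to detect a standardized effect size of 0.69, with 5% significance level and 80% power". None of these ties the 0.69 to a particular scale.

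Under the section 12.11 heading, "Description of procedures for multiplicity control and adjustment of error probabilities, if applicable", the entry is that this does not apply. Section 12.7 makes the same entry for pass/fail criteria.

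**The concern.** The main objective in section 7.2, under a superiority heading, is efficacy on knee pain, and two measures are put forward as primary evidence for it. One significance level and one power figure describe a single test of a single outcome. With two outcomes, their meaning depends on the rule that turns two results into one conclusion: success on either, success on both, or a fixed order. The protocol gives no such rule and states that multiplicity control does not apply. This is an entry made in the protocol, not a detail deferred to an analysis plan.

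At stake is how the result can be read. If one scale reaches p<0.05 and the other does not, the protocol does not say whether efficacy has been shown. The pilot aim is affected too: section 12.5.7 promises the variability of the primary outcome for a later trial without saying which outcome that is.

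**Working it through.** **Inputs from the protocol.** 35 complete participants per arm (12.5.6, 12.5.7); 1:1 allocation (12.5.5); standardized effect 0.69 (12.5.4, 12.5.7); 5% level and 80% power (12.4).

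**Assumptions.** The test is two-sided (sidedness is not stated; a one-sided 5% test would give 88.7% power, so two-sided fits the stated 80% better). The correlation ρ between the two test statistics is not in the protocol and is shown from 0 to 0.9. Where power on both measures is computed, the true effect is taken as 0.69 on each. The comparison is a two-sample t-test at one time point; power for the planned mixed model cannot be checked because no within-person correlations are given.

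**Step 1. The protocol's own figure.** Noncentrality = 0.69 × √(35/2) = 2.886, with 68 degrees of freedom.
- Two-sided 5%: critical t = 1.995, power = 81.2% (82.3% by the normal approximation).
- The effect detectable with 80% power at 35 per arm is 0.68.
- Recruitment: 70 / (1 − 0.125) = 80.

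The stated figures therefore reproduce for one outcome tested once.

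**Step 2. Either measure counts, each at unadjusted 5%.** Familywise error = 1 − P(|Z₁| < 1.96 and |Z₂| < 1.96), with Z₁ and Z₂ bivariate normal. At ρ = 0 this is 1 − 0.95² = 9.75%.

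| ρ | Familywise error | Power for at least one success |
|---|---|---|
| 0 | 9.75% | 96% |
| 0.5 | 9.1% | 92% |
| 0.7 | 8.35% | 90% |
| 0.8 | 7.8% | 88% |
| 0.9 | 7.0% | 86% |

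The power column is 2 × 0.812 minus the joint power in step 4. Error rises above 5%; power does not fall.

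**Step 3. Bonferroni, 2.5% per measure.** Critical t = 2.292.
- Power per measure at 0.69 = 72.3%.
- Detectable effect at 80% power = 0.75.
- Keeping 0.69 at 80% per measure needs 42 per arm: 84 complete, and 84 / 0.875 = 96 recruited.

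The 72.3% applies to each measure. The chance of success on at least one, if the effect is 0.69 on both, is 1 − (1 − 0.723)² = 92% at ρ = 0, 81% at ρ = 0.8 and 78% at ρ = 0.9.

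**Step 4. Both must succeed, each at 5%.** Joint power is the bivariate normal probability with each margin set to the t-based 81.2%. At ρ = 0 it is 0.812² = 66%.

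| ρ | Power for both |
|---|---|
| 0 | 66% |
| 0.5 | 70% |
| 0.8 | 74% |
| 0.9 | 76% |

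The 5% error rate is held, and power is below 80% throughout. (The normal approximation, with a margin of 82.3%, gives 68% to 78%.)

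**Step 5. One named primary, the other tested only if the first succeeds.** The error rate across the pair stays at 5%, and power for the primary stays at 81% with N unchanged.

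**The case against.** The strongest reply is that this is a pilot. The synopsis and section 3 give its purpose as estimating variability for a later trial, N=70 has a separate precision rationale in 12.5.7, reporting follows the CONSORT pilot extension, and 12.5.1 leaves effect sizes to be explored. Both scales address one pain hypothesis. All of this stands and lowers the severity. It does not remove the point: efficacy is the stated main objective, and 12.5.7 makes the 5% and 80% claim first and adds the precision rationale to it.

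Four stronger readings are tempting and are not supported.
- *That the 5% and the 80% both fail.* Among the rules worked through, none breaks both. Unadjusted either-counts raises error and keeps power; Bonferroni or both-required holds error and lowers power.
- *That the protocol tests each measure at 5%.* It does not say so. This is the natural reading of plural outcomes, one level and no adjustment, but 12.7 sets no success rule.
- *That four VAS follow-ups add further multiplicity.* Section 12.3 plans one mixed model over the repeated measures and describes no choice among visits; naming the exact contrast may be left to an analysis plan.
- *That the false-claim rate doubles.* That needs correlation near zero, which is unlikely for two self-reported pain scales in the same people. At 0.7 to 0.9 the error is 8.35% to 7.0%, and about half of it, 4.2% to 3.5% against a nominal 2.5%, would be a false claim of benefit.

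A further fair point is that Bonferroni with either-counts can still give 80% for at least one success. This requires a true effect of 0.69 on both scales and a correlation no higher than about 0.8, neither of which the protocol states.

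**Conclusion.** The point holds in a limited form. The sample-size arithmetic is correct for a single outcome, but the protocol lists two, fixes no hierarchy or decision rule, and declares multiplicity control not applicable. For an efficacy claim resting on both measures, 5% and 80% at 0.69 cannot both be assured. The cost is either a familywise error of about 7% to 9.75%, or power of about 72% per measure (detectable effect 0.75) under Bonferroni, or about 66% to 76% if both must succeed. The ranges rest on assumed correlations from 0.9 down to 0 and on a single-time-point comparison. Severity is moderate: it should be settled before unblinded data are seen, but the pilot purpose keeps it from being critical.

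**What to change.** In the synopsis, 8.3 and 12.11, name one measure as the single primary. Make the other a key secondary, tested at two-sided 5% only if the primary is significant. The VAS is the natural candidate: it is the eligibility measure (9.1) and is collected at baseline and every follow-up, whereas Table 1 has WOMAC only at baseline and week 12. The choice remains the sponsor's. Take the treatment contrast from the mixed model already planned in 12.3, for example at week 12, and make the singular and plural references agree. The stated 0.69, 80% and N=70 then stand.

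If both measures stay primary, replace the entry in 12.11 with the chosen rule and restate the power: for example, 2.5% each with a detectable effect of 0.75, or both required with the joint power and its assumed correlation.

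The first option changes wording only and leaves recruitment as it is; the demoted measure loses equal standing. If a week-12 contrast is chosen, the text of 12.3 should say so, since it narrows the longitudinal comparison now described.

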9.3 Criteria and procedures for subject withdrawal or lost to follow-up

9.3.1 When and how to withdraw a subject from the clinical investigation or stop the use of the investigational device

We anticipate participants will be enrolled in the study until the end of the study period (12 weeks home use of the garment with wired TENS).

Participants may withdraw from the study at any time of their own volition. For participants who wish to withdraw, we will record the reason (e.g. no improvement in their pain relief, increasing pain when using TENS, no reason provided, adverse events)

Participants can withdraw from the study, but data obtained up until the point of withdrawal to be retained for use in the study analysis. No further data or samples would be collected after withdrawal.

9.3.2 Documentation of efforts to be made to trace subjects that are lost to follow-up and possible reasons

Not applicable

9.3.3 Whether and how subjects are to be replaced.

We will not replace subjects.

9.4 Point of enrolment.

There are several recruitment pathways to this study. Patients who attend a knee orthopaedic clinic will be given a patient information sheet about the study by NHS staff, or the research nurse who may be in attendance to answer any questions. NHS staff may also screen current waiting lists for knee replacement surgery and forward information about the study to potentially eligible patients. Those individuals who have

read the PIS and are interested in the trial will be invited to contact the research team by phone or e-mail. GP practices may also identify patients who appear eligible with an invitation letter to take part in the trial, and a leaflet with basic information on the study and contact details. Those who contact us will be e-mailed the patient information sheet and consent form.

People interested in the study who contact the research team will be asked some questions to determine if they are likely to comply with the eligibility criteria.

Participants will then be invited to attend a formal screen clinic where an informed consent form will be completed and participants will be enrolled in the study.

